7.1.3. Population of Interest

The primary pharmacokinetic analyses will be based on the “Pharmacokinetic” population, unless otherwise specified.

7.1.4. Strategy for Intercurrent (Post-Randomization) Events

Two intercurrent events have been identified and will be handled by differing strategies:

- A *while on treatment* strategy will be employed for treatment discontinuation from nemoralisib (i.e. treatment discontinuation prior to dosing with nemoralisib on day 5 of period 2).
- A *hypothetical* strategy will be employed for treatment discontinuation from itraconazole (i.e. treatment discontinuation after dosing with nemoralisib on day 5 of period 2).

7.1.5. Statistical Analyses / Methods

Details of the planned displays for nemoralisib PK data are provided in [Appendix 8: List of Data Displays](#), and will be based on GSK Data Standards and statistical principles.

Unless otherwise specified, endpoints / variables defined in Section [7.1.1](#) will be summarised using descriptive statistics, graphically presented (where appropriate) and listed. Subjects with greater than 20% extrapolated $AUC(0-\infty)$ will be flagged.

7.1.5.1. Statistical Methodology Specification

The following pharmacokinetic statistical analyses for nemoralisib will only be performed if sufficient data is available (i.e. if participants have well defined plasma profiles). If $AUC(0-\infty)$ is not calculable for more than 50% of subjects in the PK population in each period, $AUC(0-t)$ will also be analysed for nemoralisib as described below.

Endpoint / Variables

 • $AUC(0-\infty)$ for nemoralisib • C_{max} for nemoralisib
Model Specification

 • The parameters $AUC(0-\infty)$ and C_{max} will be \log_e transformed and analysed separately using mixed effects models. • Treatment Group will be fitted as a fixed effect and subject as a random effect. • The MIXED procedure in SAS will be used with the following options:- 
 ○ The Kenward and Roger method for approximating the denominator degrees of freedom to correct for bias in the estimated variance-covariance. • Nemoralisib co-administered with itraconazole will be compared to nemoralisib administered alone.
Model Checking & Diagnostics

 • Distributional assumptions underlying the models used for analysis will be examined by obtaining box plots and normal probability plots of the studentised residuals and plots of the residuals versus the fitted values (i.e. checking the normality assumption and constant variance assumption of the model respectively) to gain confidence that the model assumptions are reasonable.
Model Results Presentation

 • For each PK parameter:- 
 • Adjusted geometric means and 90% confidence intervals (CI) for each treatment group and standard error (\log_e scale).

- Point estimates and associated two-sided 90% confidence intervals for the ratio of nemiralisib co-administered with itraconazole to nemiralisib administered alone (obtained by back-transforming estimates and 90% CIs for the treatment differences from the statistical model on the \log_e scale) and standard error (\log_e scale).
- The mean squared error (MSE) will also be presented.

7.2. Secondary Pharmacokinetic Analyses

7.2.1. Endpoint / Variables

7.2.1.1. Drug Concentration Measures

Itraconazole and hydroxy-itraconazole drug concentration data will be displayed as detailed in [Appendix 3: Data Display Standards & Handling Conventions](#) (Section 11.3.3 Reporting Standards for Pharmacokinetic).

7.2.1.2. Derived Pharmacokinetic Parameters

The itraconazole and hydroxy-itraconazole plasma pharmacokinetic parameters listed below will be calculated in the same manner as nemiralisib pharmacokinetic parameters – see Section [7.1.1.2](#).

Parameter	Parameter Description
AUC(0-∞)	Area under the concentration-time curve from zero time (pre-dose) extrapolated to infinite time. $AUC(0-\infty) = AUC(0-t) + C(t)/\lambda_z$.
AUC(0-t)	Area under the concentration-time curve from time zero to the time of the last quantifiable concentration
%AUCex	Percentage of $AUC(0-\infty)$ obtained by extrapolation
Cmax	Maximum observed plasma concentration
tmax	Time to Cmax
t _{1/2}	Apparent terminal half-life. $t_{1/2} = \ln 2/\lambda_z$

NOTES:

- Additional parameters may be included as required.
- λ_z is the terminal phase rate constant

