**Period 2:**

- There will be a washout of at least 14 days between the administration of nemiralisib in Period 1 and the administration of nemiralisib in Period 2.
- Participants will be admitted to the clinical research unit on Day -1 and will remain in-house until collection of the final PK sample on Day 11.
- From Day 1 to 10 inclusive, participants will receive a single dose of 200 mg itraconazole in the morning.
- On Day 5, participants will receive a single dose of 100 mcg nemiralisib one hour after the dose of 200 mg itraconazole.

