**Table 3 Period 2**

Procedure	Treatment Period Days												Notes
	-1	1	2	3	4	5	6	7	8	9	10	11	
Admission	X												
Discharge												X	
Alcohol breath test & drug screen	X												Includes urine cotinine test
Brief physical examination	X											X	
Laboratory assessments (hematology, clinical chemistry and urinalysis)	X										X		Pre-dose at all timepoints. Day -1 results to be reviewed before dosing on Day 1.
Clinical chemistry only			X		X		X		X				Pre-dose at all timepoints. Day 4 results to be reviewed before itraconazole dosing on Day 5.
12-lead ECG		X	X		X		X		X		X		Single measurement. Pre-dose and 3h post-dose (itraconazole) on Day 1. Pre-dose at all other timepoints, Day 4 results to be reviewed before itraconazole dosing on Day 5.
Vital signs		X	X		X		X		X		X		Single measurement. Pre-dose at all timepoints
Study treatment (itraconazole)		X	X	X	X	X	X	X	X	X			Approx. 1 h post standard meal.
FEV 1					X								Triuplicate
Inhaler (Ellipta) training					X								Training conducted by reviewing the Patient Information Leaflet with the participant. Additional training may be conducted at the discretion of the investigator.
Study treatment (nemiralisib)						X							1 h post itraconazole administration.
PK (nemiralisib)						X	X	X	X	X	X	X	pre-dose, and 5 min, 30 min, 2 h, 6 h, 12 h, 24 h, 48 h, 72 h, 96 h, 120 h and 144 h post-dose (nemiralisib)

Procedure	Treatment Period Days											Notes
	-1	1	2	3	4	5	6	7	8	9	10	
PK (itraconazole + hydroxy-itraconazole)		X				X	X					Pre-dose, 30 min, 1 h, 1.5 h, 2 h, 3 h, 4 h, 6 h, 8 h, 12 h post-dose (itraconazole) on Day 1  Pre-dose, 30 min, 1 h, 1.5 h, 2 h, 3 h, 4 h, 6 h, 8 h, 12 h and 24 h hours post-dose (itraconazole) on Day 5
AE review		←=====→										
SAE review	X	←=====→										
Concomitant medication review	X	←=====→										

- The timing and number of planned study assessments, including safety and pharmacokinetic assessments may be altered during the course of the study based on newly available data (e.g., to obtain data closer to the time of peak plasma concentrations) to ensure appropriate monitoring.

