### 10.3.1. Pharmacokinetic Analyses

All PK analyses will be performed on the Pharmacokinetic Population.

Endpoint	Statistical Analysis Methods
Primary	
Plasma nemiralisib concentration-time data will be analysed by non-compartmental methods using WinNonlin. Calculations will be based on the actual sampling times recorded during the study.
 
From the plasma concentration-time data, the following pharmacokinetic parameters will be determined for both Day 1 in period1 and Day 5 in period 2, as data permit: maximum observed plasma concentration (Cmax), time to Cmax (Tmax), area under the plasma concentration-time curve [AUC(0-t) and AUC(0-∞)], terminal half life (t1/2) and the percentage of extrapolation for AUC(0-∞).
 
Pharmacokinetic concentration data will be presented in graphical and/or tabular form.
 
Derived pharmacokinetic parameters will be listed [subjects with greater than 20% extrapolated AUC (0-∞) will be highlighted] and descriptive statistics (n, arithmetic mean, SD, 95% CI, minimum, median and maximum) will be calculated for all pharmacokinetic parameters by treatment.
 
In addition, for loge-transformed variables the geometric mean with associated 95% CI, SD on loge-scale and between subject coefficient [%CVb (100 * √(exp(SD2) - 1))] will be provided, where the SD is the standard deviation of loge transformed data.
 
To estimate the ratio of exposure of nemiralisib administered alone and co-administered following repeat doses of itraconazole, mixed effects analyses will be performed for both loge transformed Cmax and loge transformed AUC(0-∞). The geometric mean ratios will be provided along with 90% confidence intervals and the mean squared error (MSE).

Secondary	
Plasma itraconazole concentration-time data and PK parameters [Cmax, Tmax, AUC(0-t), AUC(0-∞) and t1/2] for both Day 1 (first dose of itraconazole) and Day 5 (5th Day of dosing Itraconazole or steady state) in period 2, will be analysed, listed and summarised as described for nemiralisib.
 
No formal statistical analysis will occur.

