7.2.4. Statistical Analyses / Methods

Details of the planned displays are provided in [Appendix 8: List of Data Displays](#) and will be based on GSK Data Standards and statistical principles.

Unless otherwise specified, endpoints / variables defined in Section [7.2.1](#) will be summarised using descriptive statistics, graphically presented (where appropriate) and listed. Subjects with greater than 20% extrapolated AUC(0-∞) will be flagged.

No formal statistical analysis will be performed.

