2.8.	PK	PK03	Summary of Untransformed Derived Hydroxy Itraconazole Plasma Pharmacokinetic Parameters (Period 2)	
Don't include 95% CI.
 
Still include treatment group as a variable.
 
Include variable 'day'.
 
If any NC values, include n* column and add footnote: 'NOTE: n*=number of NC values'.
 
Include footnote: 'Nemiralisib was administered on Day 5 of Period 2.'
	SAC
2.9.	PK	PK05	Summary of Log-transformed Derived Hydroxy Itraconazole Plasma Pharmacokinetic Parameters (Period 2)	
Include all parameters except %AUCex and tmax
 
Still include treatment group as a variable.
 
Include variable 'day'.
 
If any NC values, include n* column and add footnote: 'NOTE: n*=number of NC values'.
 
Include footnote: 'Nemiralisib was administered on Day 5 of Period 2.'
	SAC
2.10.	PK	Non Standard PK_T1	Summary of Statistical Analysis of Derived Nemiralisib Plasma AUC(0-inf) and Cmax	
AUC(0-inf) and Cmax only (unless AUC(0-t) also analysed)
 
Include MSE
 
Include n* and footnote (in shell) if there are any NC values
	SAC

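### Day 5 AUC(0-∞) for itraconazole and hydroxy-itraconazole uses a single-dose formula during daily dosing, and AUC(0-t) covers unequal windows on Day 1 and Day 5

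*SAP*

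**What the plan says.** **Parameters.** Protocol sections 1 and 4 and SAP 2.2 list AUC(0-∞), AUC(0-t), Cmax, tmax and half-life as secondary endpoints for itraconazole and hydroxy-itraconazole. SAP 7.2.1.2 implements this: the parameters "will be calculated in the same manner as nemiralisib pharmacokinetic parameters". AUC(0-∞) is AUC(0-t) + C(t)/λz, and AUC(0-t) runs to the last quantifiable concentration. A note adds "Additional parameters may be included as required", but no AUC(0-24), AUC(0-τ) or AUC(0-12) is named for either analyte.

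**Days.** Protocol 10.3.1 derives the itraconazole parameters on Day 1 and on Day 5, which it describes as the fifth "Day of dosing Itraconazole or steady state) in period 2". That section does not name the metabolite. SAP Tables 2.6-2.9 carry a day variable for both analytes, which implies the same two days.

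**Dosing.** The protocol synopsis states: "From Day 1 to 10 inclusive, participants will receive a single dose of 200 mg itraconazole in the morning".

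**Sampling.** In the protocol's Schedule of Activities (Table 3), the last times are "8 h, 12 h post-dose (itraconazole) on Day 1" and "12 h and 24 h hours post-dose (itraconazole) on Day 5".

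**Analysis.** SAP 7.2.4 says "No formal statistical analysis will be performed" and flags values with more than 20% extrapolation.

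**The concern.** AUC(0-t) + C(t)/λz measures total exposure from one dose only if nothing is in the circulation beforehand and nothing is given afterwards. That fits nemiralisib in each period. It does not fit the fifth of a run of daily itraconazole doses.

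Itraconazole is given only in Period 2, under one regimen, so the contrast that Tables 2.6-2.9 put before the reader is Day 1 against Day 5. The AUC(0-t) rows then carry one label over windows that differ twofold in nominal length.

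Protocol 5.1 wants precise itraconazole and hydroxy-itraconazole pharmacokinetics to support any interaction seen and for later in silico work. A reader who takes Day 5 AUC(0-∞) as inhibitor exposure would overstate it. A reader who compares AUC(0-t) across days would overstate accumulation.

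**Working it through.** The plan states no figure to reproduce here. The check has two parts.

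**1. What follows without kinetic assumptions**

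- Day 5 AUC(0-∞) = AUC(0-24) + C(24)/λz when the 24 h sample is quantifiable. The second term is positive, so the value exceeds AUC(0-24). It represents time after the next dose is due.
- Drug remaining from Days 1-4 contributes to both terms, so the value also exceeds the exposure from the fifth dose alone.
- The nominal AUC(0-t) span is 12 h on Day 1 and 24 h on Day 5. Any exposure between 12 h and 24 h is counted on Day 5 only.

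**2. Size, under stated assumptions**

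The documents give no itraconazole half-life or absorption rate. Assumed: linear one-compartment parent kinetics; doses at 0, 24, 48, 72 and 96 h; half-life T of 12, 24, 36 or 48 h; input either bolus or first-order with ka 1.0, 0.5 or 0.3 per h. That gives 16 scenarios. Hydroxy-itraconazole was not modelled.

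With bolus input the formulas are closed. Let r = 2^(-24/T) and S = (1 - r^5)/(1 - r).

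- Day 5 AUC(0-∞)/AUC(0-24) = 1/(1 - r)
- Day 5 AUC(0-∞)/single-dose AUC(0-∞) = S
- Inflation from unequal windows = Day 5 AUC(0-24)/AUC(0-12) = 1 + √r
- Day 5/Day 1 AUC ratio = S over a common 0-12 h, and S(1 + √r) over the planned windows

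| T (h) | r | AUC(0-∞)/AUC(0-24) | S | 1 + √r | Planned-window ratio |
|---|---|---|---|---|---|
| 12 | 0.250 | 1.33 | 1.33 | 1.50 | 2.00 |
| 24 | 0.500 | 2.00 | 1.94 | 1.71 | 3.31 |
| 36 | 0.630 | 2.70 | 2.43 | 1.79 | 4.37 |
| 48 | 0.707 | 3.41 | 2.81 | 1.84 | 5.17 |

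For example, at T = 12 h: r = 2^(-2) = 0.25, so 1/(1 - 0.25) = 1.33 and 1 + √0.25 = 1.50.

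Slower absorption raises these ratios. Across all 16 scenarios (exact areas):

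- Day 5 AUC(0-∞)/AUC(0-24): 1.33 to 3.56
- Day 5/Day 1 AUC over a common 0-12 h: 1.33 to 3.57
- The same ratio over the planned windows: 2.00 to 6.90
- Inflation from the windows alone: 1.50 to 1.94
- Day 5 AUC(0-24)/single-dose AUC(0-∞): 0.81 to 1.00

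Non-compartmental calculation at the scheduled times, requiring at least three points after the peak for λz, gives a Day 5 AUC(0-∞) in 15 of the 16 scenarios. The extrapolated share is then 25% to 72%, so the 20% flag would be raised in all 15.

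**The case against.** The strongest reply is that the plan already contains most of what is asked, and much of it stands.

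- **The missing measure is produced.** Day 5 AUC(0-t) is AUC(0-24) whenever the 24 h sample is quantifiable, and it appears in the same tables. A reader might infer that dosing-interval exposure cannot be recovered; the documents do not support that. What is missing on Day 5 is the name and the choice of measure.
- **The 20% flag limits the damage.** Since AUC(0-∞) = AUC(0-t)/(1 - extrapolated fraction), an unflagged value is at most 1/0.8 = 1.25 times AUC(0-t), whatever the half-life. Listings 38 and 39 mark flagged values. But the flag signals extrapolation. It says nothing of carry-over from earlier doses or of unequal AUC(0-t) windows.
- **Non-calculable values are covered.** With Day 1 sampling ending at 12 h, a reader might infer that poorly defined terminal slopes are unhandled. SAP 7.1.1.2, which governs these analytes by cross-reference, derives parameters only where the data allow, and Tables 2.6-2.9 provide for non-calculable values. No further rule is needed on this point.
- **Leaving the extrapolated percentage out of Tables 2.7 and 2.9 is not a defect.** Those are log-transformed summaries, and the untransformed Tables 2.6 and 2.8 do not exclude it.
- **The harm depends on a reader's use.** No Day 5/Day 1 ratio is planned, and no text names Day 5 AUC(0-∞) as the inhibitor exposure. This keeps the point small.

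The SAP's permission to add parameters does not answer the point, because it commits to none.

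**Conclusion.** Wrong as written, and minor. The stated rule gives a Day 5 AUC(0-∞) that is neither single-dose nor dosing-interval exposure, and AUC(0-t) rows that cannot be compared between days.

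The direction is free of kinetic assumptions. The sizes, about 1.3-3.6 times for AUC(0-∞) against AUC(0-24) and about 1.5-1.9 times for the window mismatch, rest on an assumed parent half-life of 12-48 h and linear one-compartment kinetics. They illustrate the effect and are not estimates for this trial or for the metabolite.

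A reader might infer that the interaction result itself is compromised. It is not: the primary nemiralisib ratios use none of these parameters. Cmax, tmax and any modelling from the listed concentrations are also unaffected.

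**What to change.** In SAP 7.2.1.2, 7.2.2 and the affected displays:

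1. Name AUC(0-24) as the Day 5 exposure measure for itraconazole and hydroxy-itraconazole.
2. Report AUC(0-12) on both days for any comparison between days.
3. Drop Day 5 AUC(0-∞), or keep it only with a footnote that it is neither single-dose nor dosing-interval exposure.
4. Record the change in SAP 2.1, which now reports no changes from the protocol's planned analysis.

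The cost is SAP wording and minor reprogramming of Tables 2.6-2.9 and Listings 38-39. The existing schedule supplies every sample needed. The one loss is that a listed secondary parameter is relabelled or removed on Day 5.

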7.2.2. Summary Measure

The parameters for treatment comparisons are AUC(0-∞), AUC(0-t), Cmax, tmax and t_{1/2} for both itraconazole and hydroxy-itraconazole.

7.2.3. Population of Interest

The secondary pharmacokinetic analyses will be based on the “Pharmacokinetic” population, unless otherwise specified.

7.2.4. Statistical Analyses / Methods

Details of the planned displays are provided in [Appendix 8: List of Data Displays](#) and will be based on GSK Data Standards and statistical principles.

Unless otherwise specified, endpoints / variables defined in Section [7.2.1](#) will be summarised using descriptive statistics, graphically presented (where appropriate) and listed. Subjects with greater than 20% extrapolated AUC(0-∞) will be flagged.

No formal statistical analysis will be performed.

8. SAFETY ANALYSES

The safety analyses will be based on the “Safety” population, unless otherwise specified.

8.1. Adverse Events Analyses

Adverse events analyses including the analysis of adverse events (AEs), Serious (SAEs) and other significant AEs will be based on GSK Core Data Standards. The details of the planned displays are provided in [Appendix 8: List of Data Displays](#).

8.2. Adverse Events of Special Interest Analyses

Post-inhalation cough immediately following dosing is an adverse event of special interest (AESI). This will be captured if a participant reports it as an AE. The details of the planned displays are provided in [Appendix 8: List of Data Displays](#).

8.3. Clinical Laboratory Analyses

Laboratory evaluations including the analyses of Chemistry laboratory tests, Hematology laboratory tests, Urinalysis, and liver function tests will be based on GSK Core Data Standards. The details of the planned displays are in [Appendix 8: List of Data Displays](#).

8.4. Other Safety Analyses

The analyses of non-laboratory safety test results including ECGs and vital signs will be based on GSK Core Data Standards, unless otherwise specified. The details of the planned displays are presented in [Appendix 8: List of Data Displays](#).

9. PHARMACOKINETIC (POPPK)/ PHYSIOLOGICALLY-BASED PK (PBPK) ANALYSES

The study has been designed to capture the NCA pharmacokinetics of nemoralisib alone and when in the presence of itraconazole, to measure the effect, if any, on nemoralisib exposure. If the effect on nemoralisib exposure is large (increased AUC exposure due to markedly decreased clearance) then the sampling regimen may not be adequate for estimation of $AUC(0-\infty)$ and a population PK or PBPK approach will be used to estimate $AUC(0-\infty)$ of nemoralisib when in the presence of itraconazole. In such case, a separate CPMS RAP will be generated to describe the modelling work prospectively.

9.1. Statistical Analyses / Methods

A summary of the planned potential population pharmacokinetic analyses are outlined below:

- Drug nemoralisib concentration-time data will be subjected to nonlinear mixed effects modelling using the program NONMEM to develop a population PK model or a PBPK approach where more appropriate.
- Individual post-hoc estimated PK parameters will be summarised descriptively.
- To support this analysis a PopPK dataset will be generated.

11. APPENDICES

11.1. Appendix 1: Schedule of Activities

11.1.1. Protocol Defined Schedule of Events

Table 1 Screening and Follow-up

Procedure	Screening (up to 21 days before Day 1)	Follow-up (within 5–10 days of last dose itraconazole)	Notes
Informed consent	X		
Demography	X		
Inclusion and exclusion criteria	X		
Past and current medical conditions	X		
Medical history (includes substance usage)	X		Substances: Drugs, Alcohol, tobacco and caffeine
Physical examination	X	X	Full examination (including height and weight) at screening, brief examination at follow-up
Vital signs	X		TriPLICATE
12-lead ECG	X	X	TriPLICATE
FEV ₁ and FVC	X		TriPLICATE
Laboratory assessments (hematology and clinical chemistry)	X	X	
Urinalysis	X		
HIV, Hepatitis B and C screening	X		If test otherwise performed within 3 months prior to first dose of study treatment, testing at screening is not required
Alcohol breath test & drug screen	X		Includes urine cotinine test

Procedure	Screening (up to 21 days before Day 1)	Follow-up (within 5–10 days of last dose itraconazole)	Notes
SAE review	X	X	
AE review		X	

ECG: Electrocardiogram, FEV1: Forced expiratory volume in 1 second, FVC: Forced vital capacity, HIV: Human immunodeficiency virus, AE: Adverse event, SAE: Serious adverse event.

Table 2 Period 1

Procedure	Treatment Period Days							Notes
	-1	1	2	3	4	5	6	
Admission	X							
Discharge							X	
Alcohol breath test & drug screen	X							Includes urine cotinine test
Laboratory assessments (hematology, clinical chemistry and urinalysis)	X						X	Day -1 results to be reviewed before dosing on Day 1
Brief physical examination	X						X	
Inhaler (Ellipta™) training	X							Training conducted by reviewing the Patient Information Leaflet with the participant. Additional training may be conducted at the discretion of the investigator.
FEV ₁	X							Triuplicate.
12-lead ECG		X					X	Single measurement. Pre-dose on Day 1.
Vital signs		X					X	Single measurement. Pre-dose on Day 1.
Study treatment (nemralisib)		X						
Pharmacokinetic (PK) (nemralisib)		X	X	X	X	X	X	pre-dose, and 5 min, 30 min, 2 h, 6 h, 12 h, 24 h, 48 h, 72 h, 96 h and 120 h post-dose
AE review		←=====→						
SAE review	X	←=====→						
Concomitant medication review	X	←=====→						

Table 3 Period 2

Procedure	Treatment Period Days												Notes
	-1	1	2	3	4	5	6	7	8	9	10	11	
Admission	X												
Discharge												X	
Alcohol breath test & drug screen	X												Includes urine cotinine test
Brief physical examination	X											X	
Laboratory assessments (hematology, clinical chemistry and urinalysis)	X										X		Pre-dose at all timepoints. Day -1 results to be reviewed before dosing on Day 1.
Clinical chemistry only			X		X		X		X				Pre-dose at all timepoints. Day 4 results to be reviewed before itraconazole dosing on Day 5.
12-lead ECG		X	X		X		X		X		X		Single measurement. Pre-dose and 3h post-dose (itraconazole) on Day 1. Pre-dose at all other timepoints, Day 4 results to be reviewed before itraconazole dosing on Day 5.
Vital signs		X	X		X		X		X		X		Single measurement. Pre-dose at all timepoints
Study treatment (itraconazole)		X	X	X	X	X	X	X	X	X			Approx. 1 h post standard meal.
FEV ₁					X								Triuplicate
Inhaler (Ellipta) training					X								Training conducted by reviewing the Patient Information Leaflet with the participant. Additional training may be conducted at the discretion of the investigator.
Study treatment (nemralisib)						X							1 h post itraconazole administration.
PK (nemralisib)						X	X	X	X	X	X	X	pre-dose, and 5 min, 30 min, 2 h, 6 h, 12 h, 24 h, 48 h, 72 h, 96 h, 120 h and 144 h post-dose (nemralisib)

Procedure	Treatment Period Days											Notes
	-1	1	2	3	4	5	6	7	8	9	10	
PK (itraconazole + hydroxy-itraconazole)		X				X	X					Pre-dose, 30 min, 1 h, 1.5 h, 2 h, 3 h, 4 h, 6 h, 8 h, 12 h post-dose (itraconazole) on Day 1 Pre-dose, 30 min, 1 h, 1.5 h, 2 h, 3 h, 4 h, 6 h, 8 h, 12 h and 24 h hours post-dose (itraconazole) on Day 5
AE review		←=====→										
SAE review	X	←=====→										
Concomitant medication review	X	←=====→										

- The timing and number of planned study assessments, including safety and pharmacokinetic assessments may be altered during the course of the study based on newly available data (e.g., to obtain data closer to the time of peak plasma concentrations) to ensure appropriate monitoring.
- Any changes in the timing or addition of time points for any planned study assessments must be documented and approved by the relevant study team member and then archived in the sponsor and site study files, but will not constitute a protocol amendment. The Institutional review board (IRB)/ Independent ethics committee (IEC) will be informed of any safety issues that require alteration of the safety monitoring scheme or amendment of the Informed consent form (ICF).

